Safety considerations for AIH: The physiological effects of AIH in humans are well studied and the methods proposed here deemed safe. Daily AIH-induced enhancements in breathing capacity, limb strength, and walking function occurred without significant adverse events in humans with chronic SCI.³²⁻³⁴ Although prolonged chronic exposure to more severe and longer duration hypoxia causes serious morbidity,³⁵ considerable data show that repetitive exposure to brief mild AIH elicits meaningful functional benefits without pathology.^{8, 36, 37} With mild AIH, the severity of hypoxemia, number of episodes, and exposure duration are low (15 episodes per day, 5 days) versus the chronic hypoxia experienced in obstructive sleep apnea (80-400 episodes per day for years^{35, 38}). Daily AIH (10 episodes/day, 7 days) showed no evidence for hypertension or weight loss⁹ or hippocampal gliosis or cell death in rats with SCI.⁸ Prior study in persons with SCI found no adverse events associated with mild exposures of single-day and dAIH (5 days), and all subjects tolerated exposures well.^{32, 33} No changes in mean arterial blood pressure or heart rate were found before and after each treatment or between baseline and the end of the exposure week. No maladaptive changes in cognitive or spasticity were found either, as measured by the Mini-Mental State Examination and Spinal Cord Assessment Tool for Spasticity.

We have taken great care and consideration in establishing a safe AIH protocol for persons with SCI. Rodent studies were developed using modest protocols of dAIH (10, 5 min episodes; 7 days^{8, 9}). In humans, we selected even more modest dosing (15, 1.5 min episodes; up to 5 days).^{32, 33} Our mild AIH dose of 1.5-min duration is based on human studies that delivered short doses of hypoxia ($\text{SaO}_2=80-85\%$) without report of adverse events.^{32, 33, 39, 40} We also based our AIH protocol on the pattern-sensitive effects of dAIH on respiratory motor control that were more dependent on the intermittency and repetition than the duration of the

DETAILED STUDY PROTOCOL

episodes.^{5, 7, 41-43} Such pattern-sensitivity is common to many models of neuroplasticity⁴⁴ including serotonin-dependent plasticity.⁴⁵ Daily exposures in rats (7 days) allowed for further amplification of the gains without eliciting maladaptive changes, such as cell death, hypertension, or weight loss.^{8,9}

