Twenty individuals with chronic (> 6 months post injury), motor-incomplete SCI (i.e., American Spinal Injury Association Impairment Scale (AIS) C or D) will be recruited for the study. Prior to the start of this clinical trial, we estimated the number of participants needed to achieve study objectives. In particular, our sample size computation focused on treatments: caffeine+dAIH versus placebo+dAIH alone. Our preliminary study on the effects of caffeine prior to single AIH sequence (vs placebo+SHAM) on 10MWT showed a decrease of $2.4s \pm 1.2s$. Under the hypothesis of an additive effect of caffeine+dAIH (vs. placebo+dAIH), we anticipate the difference in walking speed (10MWT time) change between treatments would be approximately $0.06m/s$. With $N=20$ cross-over participants (includes 17% attrition rate), a repeated measures ANOVA comparing 4 treatments across 4 time points, using pooled SD of $1.3s$ across days, will be sensitive to detect a difference at power of $1 - \beta = 0.80$ ($f=0.7$, $F_{3,12}=3.5$; $p=0.4$, $\alpha=.05$).

15. Recruitment

Our study coordinator ([name]), study physicians ([name], [name]), physical therapists, PI ([name]), and research collaborators will recruit subjects using a variety of strategies shown effective in the past. First, the team will identify potential subjects using Institutional Review Board approved resources to inform persons with SCI that are currently admitted to inpatient and outpatient settings at Spaulding Rehabilitation Hospital, Boston University Medical Center, Massachusetts General Hospital, Gaylord Hospital, Albany Medical Center, and Maine Medical Center. Subjects will be recruited by word of mouth and flyers at these facilities. This project also will have access to clinical resources at Spaulding Rehabilitation Network.

Prospective participants will be contacted initially by phone or in-person and informed of the methods, inclusion/exclusion criteria, and purpose of the study. We also will provide a description of this study on ClinicalTrials.gov (NCT02323698), as required by U.S. law. In all cases, recruitment will not be coercive, will not involve undue inducements, and will accurately reflect the study.

Potential subjects will be identified by the following sources:

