- Concealment mechanism – We will conceal the intervention allocation from the evaluators performing the assessments, treatment administrators, and the study participant.
- Implementation – The PI and biostatistician will generate the allocation sequences for the cross-over study. The trial coordinator will enroll participants and study staff who are not training or assessing the participants will assign the block randomized interventions.

11. Sample size

Twenty individuals with chronic (> 6 months post injury), motor-incomplete SCI (i.e., American Spinal Injury Association Impairment Scale (AIS) C or D) will be recruited for the study. Prior to the start of this clinical trial, we estimated the number of participants needed to achieve study objectives. In particular, our sample size computation focused on treatments: caffeine+dAIH versus placebo+dAIH alone. Our preliminary study on the effects of caffeine prior to single AIH sequence (vs placebo+SHAM) on 10MWT showed a decrease of 2.4s±1.2s. Under the hypothesis of an additive effect of caffeine+dAIH (vs. placebo+dAIH), we anticipate the difference in walking speed (10MWT time) change between treatments would be approximately 0.06m/s. With N=20 cross-over participants (includes 17% attrition rate), a repeated measures ANOVA comparing 4 treatments across 4 time points, using pooled SD of 1.3s across days, will be sensitive to detect a difference at power of $1 - \beta = 0.80$ ($f=0.7$, $F_{3,12}=3.5$; $p=0.4$, $\alpha=.05$).

12. Framework

This placebo-controlled study will examine the combined effects of caffeine and AIH results in greater walking performance than either intervention alone. However, this trial will not evaluate the potential superiority or equivalence of caffeine+AIH to standard of care treatments for persons with chronic iSCI.

13. Statistical interim analyses and stopping guidance

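### The stated 80% power is not the power for caffeine+dAIH versus placebo+dAIH: the cited pilot effect includes AIH's own effect, and neither f=0.7 nor 0.06 m/s is derived for that contrast

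*Combined protocol and SAP*

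**What the plan says.** Protocol 14 and SAP 11 (both headed Sample size) carry the same paragraph. It names the comparison of interest: "our sample size computation focused on treatments: caffeine+dAIH versus placebo+dAIH alone". AIH is given in both of those arms and only the capsule differs.

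The one empirical effect comes from a pilot with a different comparator: "Our preliminary study on the effects of caffeine prior to single AIH sequence (vs placebo+SHAM) on 10MWT showed a decrease of" 2.4 s (±1.2 s). The paragraph then assumes additivity and says "we anticipate the difference in walking speed (10MWT time) change between treatments would be approximately 0.06m/s". Protocol 12 gives the same 0.06 m/s as the minimum clinically important difference.

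The power statement itself rests on "a repeated measures ANOVA comparing 4 treatments across 4 time points, using pooled SD of 1.3s across days", with f=0.7, F(3,12)=3.5, a quantity printed as p=0.4, alpha 0.05 and power 0.80. N=20 includes 17% attrition.

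The trial gives three treatments (Protocol 16, SAP 10); placebo+SHAM is not one of them. The documents hold that AIH by itself is beneficial. Protocol 11a, under safety of AIH, says: "Daily AIH-induced enhancements in breathing capacity, limb strength, and walking function occurred without significant adverse events in humans with chronic SCI".

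**The concern.** The pilot and the sized contrast have different comparators. Placebo+SHAM contains neither active treatment, whereas placebo+dAIH contains AIH. An effect measured against the former cannot be carried over to the latter without removing what AIH does alone. The paragraph gives no AIH-alone estimate, shows no subtraction, and does not say how f was obtained.

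Caffeine+dAIH versus placebo+dAIH is central to the main hypothesis (Protocol 20, SAP 27). If caffeine shows no benefit, that result will be read against a stated 80% power. A reader needs to know which increment that 80% refers to, and the paragraph does not say.

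The power calculation also uses four treatments where three are given. Correcting that count would not by itself supply an effect for the two-treatment contrast.

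**Working it through.** **1. The plan's own figure.** With four treatments handled as groups, 12 error degrees of freedom imply 16 completers (16 − 4 = 12), and 16/(1 − 0.17) = 19.3, so 20 enrolled. The critical F(3,12) at 5% is 3.49, matching the printed 3.5. Reading the printed 0.4 as the correlation between repeated measures (an assumption):

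λ = f² × n × m / [1 + (m − 1)ρ] = 0.49 × 16 × 4 / 2.2 = 14.25, which gives power 0.77.

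An f of 0.722, which rounds to 0.7, gives 0.80. The 80% is therefore close to reproducible, as the power of a four-treatment omnibus test.

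**2. What separates the two contrasts.**

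(caffeine+AIH − placebo+SHAM) − (caffeine+AIH − placebo+AIH) = placebo+AIH − placebo+SHAM.

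The difference is AIH's own effect. The identity does not need additivity.

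**3. What f=0.7 represents.** f is the SD of the treatment means divided by 1.3 s. Four equally spaced means from 0 to 2.4 s give 2.4 × √(5/36) / 1.3 = 0.69. Now suppose that the fourth treatment is placebo+SHAM (an inference: it is the missing cell of the 2×2 and the pilot's comparator) and that effects add. The means are then 0, a, 2.4 − a and 2.4, where a is AIH's effect, and f = √{[1.44 + (a − 1.2)²]/2} / 1.3.

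| AIH share of 2.4 s | Caffeine increment | f | Omnibus power |
|---|---|---|---|
| 25% | 1.8 s | 0.73 | 0.81 |
| 50% | 1.2 s | 0.65 | 0.71 |
| 75% | 0.6 s | 0.73 | 0.81 |

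An f near 0.7 fits a caffeine increment of 0.6 s as well as it fits 1.8 s. It reflects the total spread, so it does not identify what caffeine adds.

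**4. What 0.06 m/s represents.** Over 10 m, the time saved is 10/v − 10/(v + 0.06), where v is baseline speed. No baseline speed is given.

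| Baseline speed | 0.06 m/s in seconds |
|---|---|
| about 0.47 m/s | 2.4 |
| about 0.68 m/s | 1.2 |
| about 1.0 m/s | 0.57 |

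The anticipated difference could thus equal the whole pilot effect, half of it, or about a quarter.

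**5. Power for the sized contrast.** Paired t test, 16 completers, two-sided 5% without multiplicity adjustment. I take 1.3 s as the SD of the change under each treatment and assume a within-person correlation ρ of 0.4 or 0. The SD of the difference is 1.3 × √[2(1 − ρ)], that is 1.42 s or 1.84 s. The noncentrality is increment × √16 / SD of difference; at 1.2 s it is 3.37 or 2.61.

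| Caffeine increment, AIH held constant | ρ = 0.4 | ρ = 0 |
|---|---|---|
| 1.8 s | >0.99 | 0.955 |
| 1.2 s | 0.88 | 0.68 |
| 0.8 s | 0.56 | 0.37 |
| 0.6 s | 0.35 | 0.23 |
| Detectable with 80% power | about 1.1 s | about 1.4 s |

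**The case against.** The strongest reply is that the plan does state a difference for the right contrast, 0.06 m/s, and that sizing on a minimum important difference is legitimate. That stands in part: the documents do not show that AIH's share was left in on the way from 2.4 s to 0.06 m/s. But no step links the two figures, and the power inputs are an SD in seconds and an f that fits a 2.4 s spread. A difference in m/s with no baseline speed cannot be set against that SD.

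Three stronger readings are tempting and are not supported.

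- A reader might infer that caffeine's increment must be below 2.4 s. The pilot used one AIH session and the trial gives five days of treatment, so the single-session total does not bound the five-day increment. The statement in Protocol 11a concerns daily AIH, so it does not size AIH's share in the pilot either.
- A reader might scale f=0.7 down by caffeine's share and report the resulting loss of omnibus power. In a four-treatment test that includes placebo+SHAM, AIH's effect stays inside f, and power stays at 0.71 to 0.81 for AIH shares of 25% to 75%.
- A reader might conclude that the trial is underpowered. If caffeine adds 1.2 s, paired power is 0.68 to 0.88, and at 1.8 s it exceeds 0.95.

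SAP 18 also requires 95% confidence intervals, which would show an imprecise null for what it is. That limits the harm but does not make the stated power correct.

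**Conclusion.** The point holds as a fault in the stated basis for power. The pilot effect belongs to another comparison and contains AIH's own effect, f=0.7 does not isolate caffeine's increment, and 0.06 m/s has neither a derivation nor a conversion to the unit of the SD. The 80% therefore cannot be read as the power for caffeine+dAIH versus placebo+dAIH.

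No single corrected figure can be given, because AIH's share of the pilot effect, the baseline speed and the five-day increment are all missing. Over increments of 0.6 to 1.8 s, paired power runs from 0.23 to above 0.99. This rests on 16 completers, on 1.3 s as the SD of change, on correlations of 0 to 0.4 and on an unadjusted 5% level; a Bonferroni correction would lower it. That f came from the full 2.4 s spread, and that placebo+SHAM was the fourth treatment, are inferences.

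**What to change.** Rewrite the sample-size paragraph in Protocol 14 and SAP 11, keeping N=20:

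- Say that the pilot compared caffeine plus a single AIH session with placebo+SHAM and did not estimate caffeine's increment with AIH held constant.
- State the assumed increment for caffeine+dAIH versus placebo+dAIH in the same unit as the SD. If 0.06 m/s is kept as the target, either give the SD in m/s or give the baseline speed used to convert it.
- Replace the single 80% with power for that within-person contrast over a stated range of increments and correlations, as in the last table above, and give the difference detectable with 80% power.

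The cost is one paragraph in two places, with no extra participants and no change to procedures. The downside is that the stated power becomes less favourable.

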Our study coordinator, study physicians, physical therapists, PI ([name]), and research collaborators recruited subjects using a variety of strategies shown effective in the past. First, the team identified potential subjects using Institutional Review Board (IRB) approved resources to inform persons with SCI that are currently admitted to inpatient rehabilitation/outpatient units of Spaulding Rehabilitation Hospital, Boston University Medical Center, Massachusetts General Hospital, Gaylord hospital, Albany Medical Center, and Maine Medical Center. Subjects also will be recruited by word of mouth and flyers at these facilities. Eligible subjects screened at INSPIRE Laboratory, Spaulding Rehabilitation Hospital Cambridge, MA. At the screening visit, subjects informed of this project, their potential involvement, the possible benefits, and risks, and their right to terminate participation at any time without penalty. Qualifying subjects in agreement with the study details asked to sign the informed consent and HIPAA form approved by Partners IRB. All potential subjects entered the study according to the inclusion/exclusion criteria above and following medical clearance. Experiments will be conducted at the Spaulding Rehabilitation Hospitals.

11. Interventions

- a. Intervention Procedures: This placebo-controlled study will examine the combined effects of caffeine (vs. placebo) and AIH (vs. SHAM) on walking performance in persons with chronic, iSCI. Participants will receive three combinatorial interventions in random order: placebo+AIH, caffeine+AIH, caffeine+SHAM. The order of interventions will be block randomized. The initial screening and evaluation procedures are similar for all participants. For each intervention, participants will complete up to 8 visits/intervention (1 baseline/intervention + 5 treatment days/intervention + 2 follow-up days/intervention). Participants will complete a total of 24 visits (8 visits/intervention x 3 interventions) after the initial screen. Participant enrollment and allocation will be completed during the screening visit. Baseline will be recorded up to 3 days prior to the first intervention.

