The main objective of this clinical trial is to evaluate the effects of a common, safe adenosine A_{2A} antagonist, caffeine, on recovery of walking following dAIH in persons with chronic iSCI. While highly specific A_{2A} receptor antagonists, such as MXS-3 and ZM2412385, block cross-talk in rats,¹⁷ their safety in SCI is not known. On the other hand, caffeine offers the ideal blend of known

safety, metabolism, and efficacious A_{2A} receptor antagonism.¹⁸ Even at low plasma concentrations (1-10µM) after one cup of coffee, caffeine antagonizes A_{2A} receptors,¹⁸ and the efficacy of moderate caffeine in blocking neural A_{2A} receptors is illustrated by the neuroprotective effects of regular caffeine consumption in dopaminergic transmission in Parkinson's Disease.¹⁹ Although caffeine has many neurobiological actions, caffeine's actions at physiologically relevant doses (1-100 µM), including the proposed dose of up to 6 mg/kg body weight, are mediated by adenosine receptor antagonism versus phosphodiesterase inhibition, release of intracellular calcium stores, or other site.²⁰ Our study will quantify the daily (5 consecutive days) effects of caffeine (e.g., 4 mg/kg) as an adjunctive therapy to dAIH for restoring walking function in persons with chronic iSCI. This dose has known safety in iSCI and substantial antagonism to A_{2A} receptors.^{18, 21, 22}

III. Methods: Participants, interventions, and outcomes

9. Trial Design

We will conduct a placebo-controlled, cross-over, block-randomized intervention study to assess the efficacy of daily caffeine prior to AIH on improving walking function in persons with chronic, motor-incomplete SCI.

10. Randomization

Assignment of interventions for study participants will be done using allocation sequence generation, concealment, and double-blinded implementation.

- Allocation sequence generation – This study will consist of three blocks: caffeine+AIH, caffeine+SHAM, and placebo+AIH. We will generate the blocked randomization for the study participants using a random number list randomizer (Random.org).²³ Participants will randomly receive each intervention block with a minimum of 2-week wash-out between blocks. We will analyze *post hoc* differences in age, impairment score, assistive device used, baseline lower extremity motor scores, and male-female ratio using independent t-tests.

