• Blinding Questionnaire		x	x	x	x	x			
• Weight (kg)	x						x	x	
Safety Outcomes									
• Pain (0-10)	x	x	x	x	x	x	x	x	
• Blood pressure (mmHg)	x	x	x	x	x	x	x	x	
• Heart rate (BPM)	x	x	x	x	x	x	x	x	
• Oxygen saturation (%)	x	x	x	x	x	x	x	x	
• Memory (0-30)	x	x	x	x	x	x	x	x	
Biomarkers									
• CYP1A2 Polymorphism	x								
• Caffeine serum level (mg/L)		x				x			
• Inflammation (CRP)		x			x		x		

IV. Statistical Principles

We plan to use a parametric linear mixed model since this method is sensitive to within subject changes and robust against variability, small sample sizes, and missing/unbalanced data sets as compared to other statistical models.²⁶ If the results do not meet these model assumptions, we will apply alternative non-parametric tests.

16. Level of significance

All applicable statistical tests will be 2-sided and will be performed using a 5% significance level.

17. Adjustment for multiplicity

we do not plan to adjust for multiplicity.

18. Confidence intervals

Statistical comparisons will include 95% (2-sided) confidence intervals (CIs).

19. Adherence and protocol deviations

We will record a deviation (if the even does not significantly affect a participant's rights, safety, or well-being, or trial outcomes), or a violation (if the deviation may potentially significantly impact the completeness, accuracy, and/or reliability of the trial data or that may significantly affect a patient's rights, safety, or well-being). All protocol deviations/violations will be logged, but no formal statistical testing will be performed.

Adverse events will be reported on an IRB-approved electronic Case Report Form (eCRF). Details will include the type of event, date of onset, duration, intensity, causality relationship to the study drug(s), and outcome. If an adverse event should occur, every attempt will be made to obtain as much information as possible about event evaluation and outcome. If a serious adverse event occurs, the treatment will be interrupted or discontinued at the physician investigator's discretion. All protocol deviations will be reported to the PI ([name]) and the IRB.

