We will quantify secondary measures of walking function using the timed up-and-go test (TUG, walking initiation and balance), six-minute walk test (6MWT, walking endurance). These tests capture functional ambulation as well as the ability to initiate walking, exhibit high reliability and construct validity.³⁵ Participants will perform 2 trials each of the TUG at their fastest but comfortable and safe speed with a minimum of 1-minute rest between trials. Average speed across the 2 TUG trials will be used for analyses. Subjects will perform the 6MWT once at their fastest, comfortable walking speed sustainable for 6 minutes. Distances will be recorded at 2 and 6 minutes. Participants will use their least restrictive assistive device during these walking assessments.

27. Analysis methods

We plan to analyze within-participant pre-post changes in walking speed (10MWT) for each intervention. We plan to use a parametric linear mixed model for comparing our outcome measure since this method is sensitive to within subject changes and robust against variability, small sample sizes, and missing/unbalanced data sets as compared to other statistical models.²⁶ If the results do not meet these model assumptions, we will apply alternative non-parametric tests.

All data will be managed using REDCap³⁶, MS 365 Excel 16.54 (Microsoft, USA), and MATLAB R2020a (Mathworks Inc, USA) and will be analyzed using SPSS[®] Statistics 26 (64-bit edition, IBM, USA). Descriptive statistics, including means, standard deviations and 95% confidence intervals of the within-participant pre-post change for each intervention will be calculated for all measures. The baseline characteristics of the participants will be compared using parametric and non-parametric inferencing.

Hypothesis testing: To evaluate our main hypothesis that caffeine prior to AIH enhances walking recovery, we will perform a linear mixed model with fixed effects at a significance at the p=0.05 level.³⁷ Intervention (caffeine+dAIH, caffeine+SHAM, placebo+dAIH) and time (day) will be the fixed main effects, with subject as random effect and walking speed (10MWT) as repeat measures. Differences from BL will be compared between and within interventions at D₅, F₁, and F₂.

Bonferroni corrections will be made for multiple comparisons.

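### The stated 80% power belongs to a four-treatment ANOVA with F(3,12), not to this three-intervention crossover; power for 0.06 m/s between caffeine+dAIH and placebo+dAIH is undetermined

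*Combined protocol and SAP*

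**What the plan says.** Protocol 14 and SAP 11 carry the same paragraph. It says that the computation concentrates on caffeine+dAIH against placebo+dAIH, and gives the target: "we anticipate the difference in walking speed (10MWT time) change between treatments would be approximately 0.06m/s". The power of 0.80 is then given for "a repeated measures ANOVA comparing 4 treatments across 4 time points", "using pooled SD of 1.3s across days", with N=20 including 17% attrition, f=0.7, F(3,12)=3.5, a figure printed as p=0.4, and alpha .05. The only source for an effect is a pilot: "Our preliminary study on the effects of caffeine prior to single AIH sequence (vs placebo+SHAM) on 10MWT showed a decrease of 2.4s±1.2s".

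The design is described differently everywhere else. Protocol 11 (Interventions): "Participants will receive three combinatorial interventions in random order: placebo+AIH, caffeine+AIH, caffeine+SHAM". Protocol 16 and SAP 10 (Randomization): "This study will consist of three blocks: caffeine+AIH, caffeine+SHAM, and placebo+AIH". SAP 20 (Analysis populations) lists one primary intervention and two control conditions. The model in Protocol 20 and SAP 27 (Analysis methods) reads: "Intervention (caffeine+dAIH, caffeine+SHAM, placebo+dAIH) and time (day) will be the fixed main effects".

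Three related settings are not fixed. On scale, SAP 26 defines the primary outcome in seconds, Protocol 18 says the average speed is analysed, and Protocol 12 gives the minimum clinically important difference as 0.06 m/s. On alpha, SAP 17 says "we do not plan to adjust for multiplicity", while SAP 27 applies Bonferroni. On time point, SAP 27 compares changes at D5, F1 and F2 without ranking them.

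**The concern.** A reader will take 0.80 as the chance that this crossover detects 0.06 m/s, the plan's own minimum clinically important difference, between caffeine+dAIH and placebo+dAIH. Two things stand in the way.

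- The powered design has four treatments and 3 and 12 degrees of freedom. This trial has three interventions, each received by everyone.
- Nothing links f=0.7, an omnibus effect size on an SD in seconds, to a pairwise difference in m/s. The pilot effect cannot supply the link: it comes from a single session and is measured against placebo+SHAM, a condition absent here.

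What is at stake is interpretation. If the primary contrast is not significant, an unsupported 0.80 invites the conclusion that a meaningful difference has been ruled out. The planned estimate and tests are not affected.

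**Working it through.** **1. The plan's own figure.** Inputs from SAP 11: f=0.7, df 3 and 12, alpha 0.05, N=20 with 17% attrition.

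- The critical value of F(3,12) at 0.05 is 3.490, so the printed 3.5 is a critical value.
- Completers: 20 × 0.83 = 16.6. In reverse, 16/0.83 = 19.3, which rounds up to 20.
- One layout that gives 3 and 12 df is four parallel groups with 16 people in total. Assume four measures each and read the undefined 0.4 as a correlation. Then λ = f²·N·m/(1+(m−1)ρ) = 0.49 × 16 × 4/2.2 = 14.25, and power is 0.773. It reaches 0.800 at f=0.722, which rounds to 0.7.

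The printed numbers may therefore be coherent for another design. This reconstruction is inferred; the documents do not state it.

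**2. The design actually planned.** Assume a simple within-person ANOVA with one value per intervention. With k=3 and n people the df are k−1 = 2 and (k−1)(n−1), that is 2 and 30 for n=16, or 2 and 38 for n=20. The planned mixed model's df depend on a covariance structure and df method that are not stated.

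At f=0.7 and between-period correlation 0, λ = f²·n·k:

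- n=16: 0.49 × 16 × 3 = 23.5, power 0.989.
- n=20: 0.49 × 20 × 3 = 29.4, power 0.998.

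**3. Whether f=0.7 carries over.** Assume a 2×2 layout (caffeine or placebo, AIH or SHAM) in which 2.4 s separates the extremes, with SD 1.3 s. Here f is the SD of the means divided by 1.3.

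| Assumed means (s) | f |
|---|---|
| Four: 0, 1.2, 1.2, 2.4 | 0.653 |
| Four: 0, 0.8, 1.6, 2.4 | 0.688 |
| Three, without placebo+SHAM: 1.2, 1.2, 2.4 | 0.435 |
| Three, without placebo+SHAM: 0.8, 1.6, 2.4 | 0.502 |

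So f close to 0.7 is about what four conditions give, and removing placebo+SHAM lowers it. At the two lower values the three-level test has power 0.73 to 0.85 with 16 people and 0.83 to 0.93 with 20 at correlation 0, or 0.92 to 0.98 with 16 at correlation 0.4.

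**4. Whether 0.06 m/s can be put on the 1.3 s scale.** The conversion is 10/v − 10/(v+0.06) seconds, where v is baseline speed, which the documents do not give. The table assumes values of v and takes 1.3 s as the SD of the within-person difference, also an assumption (paired t test, two-sided 0.05).

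| Assumed v (m/s) | 0.06 m/s in seconds | Power, n=16 | Power, n=20 |
|---|---|---|---|
| 0.5 | 2.14 | >0.99 | >0.99 |
| 0.8 | 0.87 | 0.71 | 0.81 |
| 1.0 | 0.57 | 0.37 | 0.46 |

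**5. What can be stated without those inputs.** The paired difference detectable with 80% power, two-sided, in units of the SD of the within-person difference:

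| Alpha | n=16 | n=20 |
|---|---|---|
| 0.05 | 0.75 | 0.66 |
| 0.05/3 | 0.90 | 0.78 |
| 0.05/9 | 1.04 | 0.90 |

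The divisors 3 and 9 are assumed counts: three pairs of interventions, at one or at three time points.

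**The case against.** The strongest reply is that nothing of substance changes. N is fixed, the paragraph already describes itself as a calculation made before the trial began, and the wrong number of treatments is by itself conservative (0.99 against 0.80 at the same f). The printed figures are also close to self-consistent: the gap between 0.773 and 0.80 is explained by rounding f, so this is not an arithmetic slip. All of that stands. It limits the weight of the point, but it does not make 0.80 the power of this crossover for the contrast named.

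Three further objections also stand in part. The 2 and 30 df belong to a simple ANOVA, not to the planned mixed model; still, 3 and 12 is not the df of a three-intervention crossover with 16 to 20 people. Sixteen completers is a cautious count, because 16.6 could be taken as 17 (detectable difference 0.72 SD at 0.05) and a mixed model also uses partial data. And a detectable difference in SD units says nothing about 0.06 m/s until an SD is supplied; that is true, and it is what the plan should admit.

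Two stronger readings are tempting. One is that the trial is underpowered. The documents do not show this: under the assumptions in the working, power for 0.06 m/s runs from 0.37 to above 0.99. The other is that f=0.7 pins down a single baseline speed at which it equals 0.06 m/s. It does not, because f also depends on where caffeine+SHAM falls. If its mean equals one of the two dAIH means or lies midway between them, the match is at about 0.53 or 0.49 m/s. If it is lowest and the three means are evenly spaced, the named contrast is half the range, 0.5 × 0.7 × 1.3/0.408 = 1.11 s, and the match is at about 0.70 m/s.

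**Conclusion.** The sample size statement is wrong as written. That the 0.80 is computed for four treatments with F(3,12), while the trial compares three interventions within person, rests on the documents alone. So does the absence of any link from f=0.7 or 1.3 s to 0.06 m/s.

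Power for caffeine+dAIH against placebo+dAIH at 0.06 m/s is undetermined, and no claim that it is low can be made. The illustrative powers rest on assumed means, correlations, baseline speeds and SD of the difference; the detectable differences rest only on the number of completers and alpha. The fault lies in the stated justification for N, not in the planned analysis, and the result should be read from the 95% confidence interval promised in SAP 18. It should be corrected, but it does not threaten the trial.

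**What to change.** Keep N=20. In Protocol 14 and SAP 11, withdraw 0.80 as the power of this design. The existing calculation may remain only as a dated record of how N was chosen, labelled as made for a four-treatment design. Put in its place, for example:

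*With 20 enrolled and about 16 completing all three interventions, the paired comparison of caffeine+dAIH with placebo+dAIH in change from BL at [time point], on the [seconds or m/s] scale, has 80% power at two-sided alpha [value] to detect a difference of [x] SD of the within-person difference. Power for 0.06 m/s is not known, because no SD of that difference is available on this scale.*

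Here x is 0.75 at 0.05, 0.90 at 0.05/3 or 1.04 at 0.05/9. If earlier data supply the missing SD on the analysed scale, replace the last sentence with the power for 0.06 m/s and cite the source.

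The cost is a less favourable or less definite figure, and it goes beyond rewording two paragraphs. The sponsor must choose one time point among D5, F1 and F2, choose one scale (Protocol 12, Protocol 18 and SAP 26), and settle alpha by reconciling SAP 17 with SAP 27. No extra participants are needed.
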